#### A. PRIMARY OBJECTIVES

- 1. To examine the positive predictive value of computerized CPT or ICD9 codes for SAB through medical record review for all cases combined and by maternal age and by code
- 2. To examine the accuracy of gestational age data in claims and in birth certificate data for the purposes of identifying pregnancy start among live delivery controls, who will be matched to chart-confirmed SAB cases

3. To examine the accuracy of potential confounders in claims data for the purposes of matching SAB cases and live delivery controls

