### C. DATA SOURCES

The PRISM data sources currently consist of claims-based and administrative data from Data Partners and immunization registry data from Immunization Information Systems (IIs) in Departments of Health in 7 states and New York City. Claims-based and administrative data from Data Partners include data on demographics, diagnoses, procedures, and pharmacy dispensings. Under the protocol of a separate activity entitled "PRISM Influenza Vaccines and Birth Outcomes", methods are being developed to link maternal and infant Data Partner records and to link maternal Data Partner records and birth certificate data from Vital Events Registries in select cities and states. For the current protocol, infant claims-based data and birth certificate data will be used, if available, in the process of matching controls (i.e. deliveries) to cases (i.e., SABs) on pregnancy start date since these data sources provide more precise estimates of gestational age than maternal claims-based counterparts. Electronic data (claims-based, administrative, and birth certificate data, where available) will be used for identifying cases and controls. However, only chart-confirmed cases and controls, as well as chart-confirmed gestational age and date of SAB will be used in the final analysis.

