#### H. MATCHING POTENTIAL CONTROLS TO CHART-CONFIRMED CASES (PHASE 3)

After chart review of potential cases, we will identify 1 or more potential controls (up to a maximum of 6 controls) for every case to pursue medical charts. Controls will be matched to cases on Data Partner, age, and pregnancy start (+/- 14 days), with pregnancy start estimated initially in electronic data and chart-confirmed at a later stage. Matching on pregnancy start will address temporal trends in exposure by gestational age and calendar time by maximizing the comparability between cases and controls with respect to the gestational and calendar periods covered by the risk and control intervals. Furthermore, matching on Data Partner and, maternal age will address confounding, which might occur if these factors are associated both with SAB and with timing of vaccination. If sufficient controls are available, we will also attempt to match on other important confounding factors, including comorbidities and infections, further described later in the protocol. Conditional logistic regression will be used to account for the matching and to allow for a different underlying time trend in exposure for each case:control set, which addresses the possibility of effect modification of the exposure-period association by confounders matched upon.

The matching criteria are described in more details as follows. We will match cases to controls on pregnancy start, Data Partner, and maternal age within +/-18 months. Among potential controls, we will initially estimate pregnancy start date based on an algorithm that utilizes electronic data and that is further described in the PRISM Influenza Vaccines and Birth Outcomes Protocol. Because birth certificate data and infant claims-based codes for gestational age provide more precise estimates of gestational age than their maternal claims-based counterparts, we will link potential controls identified in Data Partner records to infant Data Partner records and/or birth certificate data. We will use claims-based codes for gestational age for infants born preterm, post-term, or after a prolonged gestation (Appendix 4). If claims-based codes for gestational age for gestational age for infants age for infants in Appendix 4 are not evident, we will assume a gestational length of 270 days.

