**PRISM Surveillance Protocol** 

## IV. ANALYSIS

#### A. ANALYSIS FOR PRIMARY OBJECTIVES (OBJECTIVES 1-3)

In Primary Objective 1, we will determine the feasibility of using claims data to identify potential cases for the proposed study. We will examine the positive predictive value of claims codes for SAB, using chart review as the "gold standard". We will estimate the positive predictive value (i.e., chart confirmed SAB cases divided by all potential SAB cases identified via claims data) overall, by maternal age group (18-24, 25-29, 30-34, and 35-39 years), and by claims codes (i.e., specific ICD9 or CPT code).

In addition to validating case status in Primary Objective 1, we will estimate the proportion of cases that need to be discarded because vaccination occurs prior to the period of interest (i.e., prior to -4 weeks gestation). We will also identify the optimal look-back period for vaccine codes in relation to SAB codes in electronic data to minimize the number of cases that need to be discarded because vaccination occurred before -4 weeks gestation. To accomplish this, we will tabulate the proportion of excluded cases due to this reason by days between vaccine and SAB codes in electronic data.

In Primary Objective 2, we will examine the accuracy of gestational age data in claims and in birth certificate data for the purposes of identifying pregnancy start among live delivery controls, who will be matched to chart-confirmed cases. We will estimate the proportion of controls that must be discarded because their chart-confirmed pregnancy start date is not within the pre-specified number of days from the case date. We will estimate the proportion of controls that must be discarded because their vaccination is determined via chart review to occur after the case's gestational age at SAB. We will also examine whether the proportion of discarded controls due to each of these two reasons differs by whether birth certificates or claims data were used to estimate pregnancy start date in electronic data. Finally, we will describe the distribution of matched case-control pairs by difference in pregnancy start date in cases and controls. We will stratify by whether birth certificates or claims data were used to estimate gestational age.

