### 3. Control selection

No controls are used in an SCCS study, though unvaccinated cases could be included to contribute information to adjustments for confounding by gestational age and calendar time. No selection bias would be introduced by including such individuals.

In a case-time-control design, all individuals are vaccinated, thus making them comparable with respect to vaccination status. Controls are used to estimate the time trend in exposure in the source population that gave rise to the cases. If controls are not representative of the time trend in exposure, bias may be introduced. However, we have maximized the comparability of cases and controls with respect to time trends in exposure by matching on Data Partner, maternal age, and pregnancy start (the latter of which addresses seasonality). We will also consider matching on other confounders if there are sufficient control matches. By using conditional logistic regression, we will allow a different time-trend in exposure for each matched case:control set, which addresses the possibility of effect modification of the exposure-period association by confounders matched upon.

As a result of the matching process, one potential source of control exclusion bias, as stated in the protocol, is the requirement that all controls be linked to infants so that we can obtain more accurate estimates of claims-based gestational age, which are needed for matching controls to cases before proceeding to chart review of controls. In doing so, mothers whose infants are not enrolled in the same health plan policy are excluded from the study. If control exclusion is related to factors that are associated with timing of vaccination, such as SES or healthcare utilization, bias may be introduced. However, such differences between excluded and included individuals are expected to be minimal, even if they exist.

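### Primary Objective 2 compares birth certificate and claims dating between different women, so its by-source discard table does not isolate the accuracy of either source

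*Protocol*

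**What the plan says.** Protocol section II.A states the second primary objective as "To examine the accuracy of gestational age data in claims and in birth certificate data", for the purpose of finding pregnancy start in live-delivery controls.

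Section IV.A gives the analysis. It reports the proportion of controls discarded for two reasons found at chart review: the chart start date is too far from the case's, or vaccination falls after the case's gestational age at the loss. It then asks whether these proportions differ "differs by whether birth certificates or claims data were used to estimate pregnancy start date in electronic data". The distribution of case-control differences in start date is handled the same way: "We will stratify by whether birth certificates or claims data were used to estimate gestational age".

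On availability, section III.C says methods are being developed to "link maternal Data Partner records and birth certificate data from Vital Events Registries in select cities and states", and that "infant claims-based data and birth certificate data will be used, if available, in the process of matching controls". Section III.H adds that "we will link potential controls identified in Data Partner records to infant Data Partner records and/or birth certificate data". It matches on pregnancy start (±14 days), Data Partner and maternal age, refers to a separate protocol for the electronic dating algorithm, and assumes 270 days when no Appendix 4 code is found. Appendix 7, under control selection, speaks of "the requirement that all controls be linked to infants so that we can obtain more accurate estimates of claims-based gestational age".

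**The concern.** The objective concerns the accuracy of two data sources. The planned comparison sorts each control into one group according to the source that supplied her electronic date. No comparison of the two sources in the same woman is described.

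Two things besides accuracy can then separate the groups. First, which source is used depends partly on where the woman lives, because certificates exist only in some places and place is not matched. Section V.B itself accepts that linked women may differ from other women with live deliveries in comorbidities or use of care, but it does not carry that caution into the source comparison. Second, a discard combines dating error with how far the electronic date already stood from the case's date.

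The overarching goal in section II is to optimize algorithms that use claims and birth certificate data. A difference in discards could be read as a difference in accuracy when the sources are equally good, or a real difference could be masked.

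**Working it through.** The protocol states no sample size, expected discard rate or power for Objective 2, so there is no figure to reproduce. The check has three steps.

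**1. Who is compared.** Objective (II.A): accuracy of both sources. Comparison (IV.A): discards split by the source used. One source per control means two separate groups of women. Certificate use is limited by place (III.C), and the matching factors (III.H) do not include place. The source used is thus tied to place, and the matching does not remove this.

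**2. What a discard measures.** Let d be the control's electronic start date minus the case's start date, and e the control's chart start date minus her electronic start date. With the ±14-day caliper of III.H, a control is discarded for start date when |d + e| > 14. Only e is dating accuracy; d is closeness of the match.

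By hand, with a fixed error e = 7 days and d uniform (assumption):
- d within ±3: the largest |d + e| is 3 + 7 = 10, so 0% are discarded.
- d within ±7: the largest is 7 + 7 = 14, so 0% are discarded.
- d within ±14: discarded when d > 7, so (14 − 7)/28 = 25%.

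The same dating error gives 0% or 25% discards according to match closeness.

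Simulation (400,000 draws). All inputs are assumptions: term length normal with mean 277 and SD 8 days; 10% preterm with mean 245 and SD 14; 80% of preterm births coded, in two-week steps; all others dated at 270 days; certificate error SD 5 days; d uniform.

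| Electronic mismatch d | Discards, certificate dating | Discards, claims dating |
|---|---|---|
| ±3 days | 0.8% | 19.6% |
| ±7 days | 2.6% | 22.0% |
| ±14 days | 14.3% | 30.4% |

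Check of one cell: for d uniform on ±14 and |e| up to 28, the discard probability is |e|/28. With SD 5, mean |e| = 5 × √(2/π) = 3.99, and 3.99/28 = 14.2%, in line with the simulated 14.3%.

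Within each column the dating method is unchanged, yet the discard proportion moves. Groups that differ in match closeness, for example because one place has fewer candidate controls, would differ in discards without any difference in accuracy. The protocol does not say whether they do differ.

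Birth mix was also varied, with d within ±14. For a preterm share of 5% to 15% (50% or 80% of preterm births coded), claims discards stayed between about 30% and 33%, and certificate discards near 14%. Under these assumptions it is a minor factor.

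**3. Whether both dates can be had for one woman.** If Appendix 7's infant-link requirement applies, every certificate-linked control also has infant claims. If the and/or wording of III.H applies, some may not, but the 270-day default still yields a claims date. Chart review supplies the reference date (III.I, III.O). Both errors can therefore be computed for certificate-linked controls. How many there are is not stated.

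**The case against.** The strongest defence is that Objective 2 is descriptive. Section III.K calls the analyses for Objectives 1-3 descriptive statistics, and no hypothesis that one source is better is set. The by-source table answers a real operational question: how many charted controls are lost under each source as used. That stands, and the table should be kept. It still does not measure what section II.A names.

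A statistical analysis plan may exist and may add adjustment. That could reduce differences by place, but the comparison that the protocol fixes is between women by source used.

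Section III.K says the team will strive for an exact match on pregnancy start. If every match were exact, d would be 0 and the closeness mechanism would vanish. The same section expects that this may not be possible, and III.H allows ±14 days.

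The paired comparison has its own weakness. Controls reach chart review because the date from the source used met the caliper and the vaccination window; the other source's date faced no such selection. This needs a caveat but does not defeat the comparison, because selection acts on the electronic date relative to the case, not directly on its error against the chart.

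A reader might infer that the source comparison is already shown to be biased by a different birth mix. The documents do not support this: they give no birth mix by source, Appendix 4 assigns 287 or 294 days to coded post-term and prolonged births, and the preterm mix had little effect above. A reader might also infer that the two groups are exactly women with and without a certificate link. That assumes certificates take precedence, and the dating algorithm sits in another protocol. Nor does the text say that this comparison determines whether linkage is built; linkage is developed under a separate activity (III.C).

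**Conclusion.** The point holds in a limited form. The planned comparison is between women, source use is tied to place, place is not matched, and the discard measure mixes dating error with match closeness. The table describes losses by source as used and does not isolate source accuracy.

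The size of any distortion cannot be computed from the protocol, which gives neither the certificate-linked share nor match closeness by source. The range of 0.8% to 14.3% at fixed certificate accuracy shows only that match closeness can matter; it rests wholly on the assumed distributions in the working. Confounding is a risk built into the design and has not been demonstrated. The change is worth making because a more direct measure is available from data already collected.

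**What to change.** For every charted control with a birth certificate link, derive two electronic pregnancy start dates: one from the certificate and one from claims (Appendix 4 code, or the 270-day default). Compare each with the chart date in the same woman, and report the paired difference in absolute error and the paired proportions with error above 14 days. Make this the Objective 2 comparison of source accuracy.

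Report the number of pairs and how many claims dates rest on the default. State that controls were selected on the date from the source used, and which source that was. Reconcile Appendix 7's infant-link requirement with the and/or wording in III.H and V.B, since this decides what a claims date means in the paired set.

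Keep the by-source discard table as an operational description, shown by Data Partner.

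The cost is one extra derived date per linked control and a short paired analysis, with no new charts. The limitation is that the paired set contains only controls with both estimates. The protocol does not give that number, and it could be small.

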If there are sufficient control numbers, we will consider matching controls to cases on diagnoses of diabetes, obesity, asthma, and multiparity based on CPT and ICD9-coded data. Finally, where information on particular time-varying confounders is available in claims-based data, we will attempt to match cases and controls on such factors if sufficient controls exist. We will attempt to match cases and controls on the presence of urinary tract infections, respiratory infections, gastrointestinal infections, sexually transmitted infections, and medically attended fever within a 1-28 day period prior to SAB/index date, identified using ICD9-coded data (Appendix 5). Finally, we will collect information from the medical record on factors not matched upon in the design phase, such as smoking, alcohol, and substance abuse, and adjust for them in regression models if feasible.

Multiparity will be identified using codes listed in Appendix 5. The algorithms for identifying obesity and diabetes are described in the PRISM Influenza Vaccines and Birth Outcomes Protocol. Asthma will be identified using an algorithm validated and developed by the Medication Exposure in Pregnancy Risk Evaluation Program (MEPREP), an FDA-sponsored collaboration between 11 health plans. To be considered asthmatic, a woman must have one of the following during the 90 days prior to pregnancy through end of pregnancy: (1)>=2 outpatient visits at least 30 days apart with ICD9 diagnosis code 493\*, (2) >=1 inpatient visit with ICD9 diagnosis code 493\*, or (3) >=1 outpatient visit with ICD9 diagnosis code 493\* and >=1 dispensing of an asthma medication (short- or long-acting beta-agonist, inhaled corticosteroid, leukotriene receptor antagonist, mast cell stabilizer, methylxanthine). This algorithm was shown to have a positive-predictive value of 95% in MEPREP.

Among potential controls meeting matching and enrollment criteria, TIV identified in claims or IIS data must be received between -6 weeks gestation and 2 weeks past the case's gestational age at SAB, with gestational age estimates from birth certificate or infant-claims based estimates. A 2-week margin before and after the gestational period of interest will be initially incorporated to allow for misclassification of gestational age in live delivery controls due to use of claims and birth certificate data for gestational age estimates.

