#### I. IDENTIFYING POTENTIAL CONTROLS IN CLAIMS-BASED AND ADMINISTRATIVE DATA (PHASE 3 AND 4)

After 2 or more potential controls are identified in electronic data for each chart confirmed case, we will then conduct a second round of chart review to confirm that these controls have vaccine exposure in the gestational period of interest (i.e., 4 weeks before pregnancy start to the index date). These potential controls will proceed to full chart review to confirm live delivery, gestational age at delivery, pregnancy start date, TIV exposure, and gestational age at vaccination. Controls will only be retained if they received TIV between -4 weeks gestation and the index date. Initially we will require controls to be continuously enrolled in the 360 days prior to delivery. This 360-day period incorporates a 90-day period prior to pregnancy start and a 270-day period, the average gestational length of a term pregnancy. Following chart review, controls will only be retained if they are determined to have enrollment 90 days prior to pregnancy start through the index date. Following chart review, if both controls in a given case-control set do not meet inclusion criteria, we will attempt to match the case to an unmatched control from a different case-control set, if available. If cases remain unmatched despite these attempts, they will only be included in analyses for Objectives 1 and 2. If both controls in a given case-control set meet inclusion criteria, we will randomly select one control.

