In Primary Objective 3, we will determine the accuracy of claims data for matching potential cases and controls on potential confounders. We will determine the positive predictive value in cases and controls for each of the confounders matched upon. We will also determine the proportion of matched case-control pairs that have concordant status in chart data for each matching factor (i.e., confounder).

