#### **B. LIMITATIONS**

Foremost, we will have limited power to detect small or modest effect sizes in this feasibility study. For example, our target sample size of 100 cases and 100 controls corresponds to approximately 80% power to detect a relative risk of 2.4 or above for the pilot objective of examining whether there is an elevated risk with exposure during the risk interval of 2-6 weeks gestation. Of note, this power calculation may be somewhat optimistic if we obtain fewer charts than originally anticipated or if a significant portion of cases or controls do not meet study inclusion criteria (e.g., not vaccinated during the period of interest), or depending on the distribution of cases and controls in 3 different gestational age risk periods. Our power calculation may also be an overestimate if our assumptions used to calculate power, such as the gestational age distribution of SAB or the gestational distribution of vaccination among controls (both of which are based on published literature), are incorrect. However, the primary objectives of this proof-of-concept protocol are to determine optimal algorithms for using claims and birth certificate data for pregnancy related studies. As such, this study will have the capability to inform future studies on pregnancy outcomes in the Mini-Sentinel.

The current study's case definition is limited to women seeking medical care for SAB. A large percentage of miscarriages occur without medical care, particularly in those occurring early during pregnancy. A significant proportion of these early pregnancies, particularly in the first six weeks, are unrecognized by the mother, making detection difficult. Thus, results may not be applicable to the effects of vaccines on

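### Primary Objective 3 rests on PPV and raw pair concordance, and for an uncommon confounder neither reveals a claims code with high PPV but low sensitivity

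*Protocol*

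**What the plan says.** Section II.A of the Protocol states the objective: "To examine the accuracy of potential confounders in claims data for the purposes of matching SAB cases and live delivery controls". Section IV.A gives the analysis in two steps. First: "We will determine the positive predictive value in cases and controls for each of the confounders matched upon". Second, the "proportion of matched case-control pairs that have concordant status in chart data for each matching factor" is to be reported. No sensitivity, negative predictive value, chance benchmark or chance-corrected agreement is named, and no threshold is set.

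The candidate factors are in section III.H. For chronic conditions and parity, if control numbers allow, "we will consider matching controls to cases on diagnoses of diabetes, obesity, asthma, and multiparity based on CPT and ICD9-coded data". For time-varying factors, an attempt will be made to match on "urinary tract infections, respiratory infections, gastrointestinal infections, sexually transmitted infections, and medically attended fever within a 1-28 day period prior to SAB/index date". The only accuracy figure for any confounder algorithm concerns asthma: "This algorithm was shown to have a positive-predictive value of 95% in MEPREP". No sensitivity accompanies it, and no prevalence is given for any factor.

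Section III.I fixes the pairing: "If both controls in a given case-control set meet inclusion criteria, we will randomly select one control". Section V.B gives the size: "our target sample size of 100 cases and 100 controls".

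**The concern.** Matching on claims status balances a confounder only as far as claims status tracks true status. For an uncommon factor, most pairs are matched on the absence of a code. Failure therefore occurs mainly among code-negative women who have the condition. PPV is computed only in code-positive women and does not see them. Raw concordance includes them, but two women who both lack an uncommon condition agree whether or not matching did anything, so the figure starts high.

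A code that misses most affected women could thus show a high PPV and a high concordance while leaving the confounder largely unmatched. Section V.B says the study is meant to inform later pregnancy work in the same system, so a favourable figure without a benchmark could be carried forward as support for claims-based matching.

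**Working it through.** The Protocol states no figure for Objective 3, so there is none to reproduce.

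**Inputs.** From the Protocol: 100 pairs, one control per case (III.I, V.B), and PPV 95%, the asthma figure in III.H, used here as an example. Assumed: chart prevalence p and claims sensitivity s, each over a range. Also assumed: exact matching on claims status, equal prevalence and accuracy in cases and controls, and chart status independent within a pair given claims status.

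**Step 1: concordance by chance.** If claims say nothing about the factor, expected concordance is p² + (1−p)².

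| Prevalence p | Chance concordance |
|---|---|
| 1% | 98.0% |
| 2% | 96.1% |
| 5% | 90.5% |
| 10% | 82.0% |
| 20% | 68.0% |
| 30% | 58.0% |

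It is 90% or more only when p ≤ (1 − √(1 − 0.2))/2 = 5.3%. With unequal prevalences, 5% in cases and 3% in controls, it is 0.05×0.03 + 0.95×0.97 = 92.3%.

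**Step 2: PPV with uninformative codes.** PPV then equals the prevalence, for example 5% at p = 5%. The planned PPV reveals this failure.

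**Step 3: high PPV, varying sensitivity, p = 5%.**
- Code-positive share: q = s·p/PPV.
- Chart-positive share among code-negatives: m = (1−s)p/(1−q).
- Concordance: q[PPV² + (1−PPV)²] + (1−q)[m² + (1−m)²].
- Share of chart-positive cases with a chart-positive control: s·PPV + (1−s)·m.
- Kappa: (concordance − chance)/(1 − chance).

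For s = 20%:
- q = 0.01/0.95 = 0.0105 and m = 0.04/0.9895 = 0.0404.
- Concordance = 0.0105×0.905 + 0.9895×0.9224 = 92.2%.
- Share = 0.20×0.95 + 0.80×0.0404 = 22%.
- Kappa = (0.9222 − 0.905)/0.095 = 0.18.

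For s = 90%:
- q = 0.045/0.95 = 0.0474 and m = 0.005/0.9526 = 0.0052.
- Concordance = 0.0474×0.905 + 0.9526×0.9896 = 98.6%.
- Share = 0.90×0.95 + 0.10×0.0052 = 86%.
- Kappa = (0.9856 − 0.905)/0.095 = 0.85.

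| Codes (p = 5%) | PPV | Concordance | Kappa | Chart-positive cases with chart-positive control |
|---|---|---|---|---|
| Uninformative | 5% | 90.5% | 0 | 5% |
| Sensitivity 20% | 95% | 92.2% | 0.18 | 22% |
| Sensitivity 90% | 95% | 98.6% | 0.85 | 86% |

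At 20% sensitivity, about 99% of pairs are matched on a negative code, and of 5 expected chart-positive cases in 100, 4 have no code.

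**Step 4: what 100 pairs can separate from chance.** This uses an exact binomial test, one-sided 0.025. At p = 5% at least 97 concordant pairs are needed.
- Sensitivity 50%, specificity 99.5%: concordance 94.3%, power 18%.
- Sensitivity 80%, specificity 99%: concordance 96.5%, power 53%.
- Sensitivity 95%, specificity 99.9%: concordance 99.3%, power 99%.

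At p = 20% the first of these codes gives 81.5% against 68.0% by chance, with power 85%.

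**The case against.** The other side has several fair points.

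- **Useless codes.** A reader might infer that good and useless codes would look alike under Objective 3. They would not, because the planned PPV would fall to the prevalence. The gap is confined to codes with high PPV and low sensitivity. This stands.
- **Prevalence.** A reader might take the floor of about 90% as general. It applies only up to about 5.3% prevalence. The Protocol gives no prevalences, and the factors include obesity and multiparity, which may well be commoner. For a common factor, low concordance would itself show that matching had failed. This stands.
- **No decision rule.** Section IV.A sets no threshold, and III.K describes the outputs for Objectives 1–3 as descriptive. Nothing in the Protocol says matching will be declared adequate at some level of concordance. This stands, but a primary objective still needs figures that a reader can interpret.
- **Left to the SAP.** Kappa and sensitivity can be seen as detail for an analysis plan not shown here. This carries less weight, because III.K sends the reader to the Protocol's own analytic section for these statistics, and that section selects two.
- **Chart data will be described anyway.** Section III.O collects several risk factors for descriptive purposes, so a reader could derive the chance figure from the chart prevalences. Sensitivity, however, needs claims and chart status cross-tabulated, and IV.A does not plan that.
- **Conditional scope.** Matching beyond Data Partner, age and pregnancy start depends on control numbers in III.H and III.K, although V.B states matching on infections without that condition. The point matters only for factors actually matched upon.

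**Conclusion.** The point holds in a limited form. For a confounder present in about 5% of women or fewer, the two planned measures can both look favourable while claims matching leaves most affected cases with an unaffected control. At an assumed 5% prevalence and PPV 95%, concordance moves only from 92.2% to 98.6% as sensitivity rises from 20% to 90%, while the share of affected cases with an affected control moves from 22% to 86%. The size depends on the assumed prevalences and the matching assumptions above. Low prevalence is plausible for infections and fever counted in a 28-day window, but the Protocol does not establish it.

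A reader might go further and infer that Objective 3 cannot show whether matching works, or that raw concordance should be dropped. The documents do not support either. Near-perfect codes are separable from chance with 100 pairs even at 5% prevalence, and concordance is the direct count of pairs left unbalanced. What it lacks is a benchmark, and what PPV lacks is sensitivity beside it.

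**What to change.** In section IV.A, Primary Objective 3, keep PPV and raw concordance. For each factor matched upon, add the following, with confidence intervals:

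1. The concordance expected by chance from the observed chart prevalences in cases (p₁) and controls (p₀), p₁p₀ + (1−p₁)(1−p₀), with kappa.
2. Sensitivity of the claims status against the chart, in cases. Cases are not selected on confounder status, whereas the controls' claims status is set by the matching.
3. As a description only, the share of chart-positive cases whose matched control is chart-positive.

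Add one sentence saying that high raw concordance alone will not be taken as evidence that claims matching works.

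The cost is wording and a few table rows. Section III.O already abstracts asthma, diabetes, obesity, febrile illness, infections and gravidity. Multiparity needs one more item, since III.O names gravidity and not parity. The downside is precision: at 5% prevalence about 5 of 100 cases are chart-positive, so items 2 and 3 and kappa will have wide intervals and look less favourable than the planned figures. For that reason they should stand beside the planned measures and not replace them.
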